Laboratory testing (blood draw, pregnancy test ⁶)		X	X ⁶		X				X	X ⁶	X ⁶
C-SSRS		X									
Post-Cessation Smoking Outcomes											
Point Prevalence Abstinence			X	X	X	X	X	X	X	X	
Timeline Follow-Back											X
Carbon Monoxide			X	X	X	X	X	X	X	X	X

Research Proposal

Saliva Cotinine										X	X
Nicotine Dependence and Withdrawal											
FTND* 6 items		X									
QSU* 10 items			X		X		X		X	X	X
MWS* 15 items			X	X	X	X	X	X	X	X	X
Smoking Abstinence Expectancies Questionnaire (SAEQ) 28 items	X	X	X		X		X		X	X	X
Smoking Cessation Self-Efficacy (SE) 43 items		X	X		X		X		X	X	X
Smoking Cue Appeal Survey (SCAS) 8 items			X								X
Barriers to Cessation Scale (BCS) 19 items		X									
Smoking Consequences Questionnaire-Brief (SCQ-Brief) 25 items		X									
Intolerance for Smoking Abstinence Discomfort (IDQ-Smoking) 17 items		X	X		X		X		X	X	X
Mood, Emotion, and Cognition											
Inventory of Depression and Anxiety Symptoms (IDAS) 64 items			X		X		X		X	X	X

Research Proposal

Difficulties with Emotion Regulation Scale (DERS) 36 items			X		X		X		X	X	X
NEO-FFI 60 items		X									
Regulatory Focus Questionnaire (RFQ) 11 items		X									
Sleep, Financial Strain, Life Stressors											
Financial Strain Questionnaire (FINSTR) 8 items		X									
Impulsivity											

Research Proposal

Delay Discount Questionnaire 27 items			X								X
UPPS 59 items			X								X
Panic Severity											
Panic Attack Questionnaire (PAQ)	X										
PDSS* 7 items		X	X	X	X	X	X	X	X	X	X
Anxiety Sensitivity, Distress Intolerance and Negative Affect											
ASI-III* 18 items		X	X	X	X	X	X	X	X	X	X
DII 10 items		X	X	X	X	X	X	X	X	X	X
PANAS*		X	X	X	X	X	X	X	X	X	X
Brief Pain Inventory			X								X
Treatment Integrity/Acceptance											
Credibility/Expectancy				X ⁴							
Therapist Adherence ¹				X	X	X	X	X	X		
Patient Adherence ²			X	X	X	X	X	X	X	X	X
Adverse Events ³		X	X	X	X	X	X	X	X	X	X
Concurrent Treatment		X	X	X	X	X	X	X	X	X	X

Research Proposal

AlcoBreath Screening ⁵					X	X	X				
Vital Signs			X								
Face Task											
Facial Recognition Task			X							X	X

Note. Shaded areas refer to measures of mediator variables. *These measures are completed as online questionnaires. ^{1,2} Patient adherence and therapist competence will be monitored separately and the schedule will vary. ³Adverse events will be assessed for DCS/PBO and NRT. ⁴Administered at the end of session 1. ⁵Alcohol screening will be completed prior to each of the three sessions which include DCS/PBO administration. ⁶The pregnancy test is the only one that will be completed at intake and monthly following randomization(SV2, 7, 13, 21, and 29). The remaining lab testing will only occur should the physician see fit.

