Our study consists of three aims: to compare, in a randomized clinical trial, (1) the effects of PSRT+DCS versus PSRT+PBO on smoking cessation outcomes and (2) the effect of PSRT+DCS vs. PSRT+PBO on the frequency and intensity of panic attacks, withdrawal symptoms, negative affect, anxiety sensitivity, and distress intolerance; and (3) to explore the

Research Proposal

mechanisms by which PSRT+DCS improves smoking cessation outcomes. We hypothesize that individuals in the PSRT+DCS condition will evidence superior smoking cessation outcomes (i.e., longer time to first smoking lapse and relapse and lower PPA) and reduced anxiety and panic symptomatology compared to those in the PSRT+PBO condition.

To achieve our aims, adult smokers with panic attacks from the Austin community will be randomly assigned to either: (1) PSRT+DCS or (2) PSRT+PBO. Primary outcome measures will be point prevalence abstinence (PPA), time to first smoking lapse, and time to smoking relapse. Proposed mediators include panic attacks, distress intolerance, anxiety sensitivity, nicotine withdrawal symptoms, and negative affect. These variables will be assessed at baseline, weekly during the treatment phase, and at 2, 4, 8, 10, 16, and 24 weeks after quit date.

The proposed study represents a crucial and important stage in translating basic research to strategies for treating nicotine dependence. The investigation addresses an important public health issue by testing an integrated intervention - informed by basic research - that may lead to a more effective and efficient treatment for at-risk smokers while simultaneously isolating explanatory mechanisms. The expected findings should: (1) guide advances in the theoretical conceptualization of the mechanisms involved in panic- and anxiety-smoking relations; and (2) provide initial effect size data for the addition of DCS to an integrated psychosocial/behavioral and pharmacological smoking cessation intervention for smokers with panic attacks, and thus provide the necessary data for a large-scale follow-up trial.

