Smoking Cue Appeal Survey (SCAS). The Smoking Cue Appeal Survey (Murray, McHugh, Rowley, Sirota, & [name], 2010) measures cue appeal to sensory smoking cues. An initial study demonstrated good psychometric properties associated with smoking status and craving (Murray et al., 2010).

Barriers to Cessation Scale (BCS). The Barriers to Cessation Scale (Macnee & Talsma, 1995) is a 19-item measure assessing barriers or specific stressors associated with smoking cessation. It has been found to have good internal consistency, good content, and predictive validity (Macnee & Talsma, 1995).

Research Proposal

Smoking Consequences Questionnaire – Brief (SCQ-Brief). The SCQ-Brief is an abbreviated version combining both the Smoking Consequences Questionnaire (SCQ; Brandon & Baker, 1991), an 80-item measure assessing positive and negative smoking outcome expectancies, and the Smoking Consequences Questionnaire - Adult (SCQ-A; Copeland et al., 1995), a 55-item measure considered to be more suitable for adults. The brief version is a 25-item measure that has shown good internal consistency and convergent validity (Rash & Copeland, 2008).

Intolerance for Smoking Abstinence Discomfort (IDQ-Smoking). The IDQ-Smoking questionnaire is a 17-item measure that assesses the intolerance of discomfort associated with recent smoking cessation. The IDQ-S has three reliable components: withdrawal Intolerance, Lack of Cognitive Coping, and Pain Intolerance.

Smoking Status. Self-reports of smoking status will be collected from participants at baseline, weekly throughout treatment and at follow-up assessments. Participant reports of abstinence at all times will be verified by expired carbon monoxide, and additionally at the 8, 10, 16, and 24-week interviews with saliva cotinine (see Table 2). The main outcome analyses are based upon 7-day point prevalence abstinence (i.e., reported abstinence of at least 7 days prior to each scheduled follow-up). Self-report will be overridden by objective verification in the conservative direction (Proceedings of the National Working Conference on Smoking Relapse, 1986).

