In addition to point-prevalence outcomes, we also will use the timeline follow-back (TLFB) procedure for assessing the time to first smoking lapse and the time to first relapse, defined as the 7th day on which smoking occurs. The TLFB procedure has demonstrated good reliability and validity (Sobell & Sobell, 1996). The TLFB will be administered at each follow-up to assess cigarette use since the previous assessment.

Biochemical Verification. Self-reported abstinence at the 8, 10, 16, and 24-week follow-ups will be verified by saliva cotinine (cutoff value of 10 mg/ml) for stated abstinence of 2 weeks or more (cotinine may be incompletely metabolized before this time), and carbon monoxide analysis of breath samples (8ppm cutoff) for stated abstinence of 24 hours to 2 weeks (Jarvis et al., 1987). Saliva samples will be frozen and analyzed by an outside laboratory for cotinine level using radioimmune assay. Expired air carbon monoxide levels will be assessed with a Vitalograph Breathco carbon monoxide monitor (Jarvis et al., 1987). Detected values above the stated cutoff scores will be considered indicative of smoking.

Mood, Emotion, and Cognition

Inventory of Depression and Anxiety Symptoms (IDAS). The IDAS is a 64-item measure assessing specific symptom dimensions of major depression and related anxiety disorders (Watson et al., 2007). The scales are internally consistent and show excellent convergent validity and good discriminant validity (Watson et al., 2007).

Difficulties with Emotion Regulation Scale (DERS). The DERS is a 36-item self-report measure of clinically-relevant difficulties in emotion regulation (Gratz & Roemer, 2004). The scale has been validated in cocaine dependent (Fox et al., 2007) and alcohol dependent (Fox, Hong, & Sinha, 2008) populations.

Research Proposal

NEO Five-Factor Inventory (NEO-FFI). The NEO-FFI is a 60-item self-report measure of five basic personality factors (Costa & McCrae, 1989). The measure has been shown to have high test-retest reliability (Robins et al., 2001) and internal consistency (Costa & McCrae, 1992).

Regulatory Focus Questionnaire (RFQ). The Regulatory Focus Questionnaire (RFQ; Higgins et al., 2001) was derived from a factor analysis of items assessing the history of individuals' success at promotion and prevention tasks over the course of their lives.

Sleep, Financial Strain, Life Stressors

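### Table 2 contradicts the text on when smoking outcomes are collected, and the stated look-back leaves the first 28 or 14 days after quitting without the day-level record needed to date relapse

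*Protocol*

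**What the plan says.** Protocol section 3 (Purpose) sets three primary outcomes: "Primary outcome measures will be point prevalence abstinence (PPA), time to first smoking lapse, and time to smoking relapse". It then gives the assessment times: "These variables will be assessed at baseline, weekly during the treatment phase, and at 2, 4, 8, 10, 16, and 24 weeks after quit date". Section 4 (Procedures) repeats both statements.

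Section 5 (Measures, Smoking Status) describes the TLFB as the "procedure for assessing the time to first smoking lapse and the time to first relapse, defined as the 7th day on which smoking occurs". No other method is named for dating either event. On timing and reach it says: "The TLFB will be administered at each follow-up to assess cigarette use since the previous assessment". Section 8 (Compensation) lists the follow-ups as protocol weeks 9, 13, 15, 21 and 29.

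In Table 2 (Schedule of assessments), the row "Timeline Follow-Back" has one mark, in the last column (WK 8, 10, 16, 24). The row "Point Prevalence Abstinence" is marked from baseline to WK 4 and is blank in that last column.

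On smoking status the text says: "Self-reports of smoking status will be collected from participants at baseline, weekly throughout treatment and at follow-up assessments". Reported abstinence is to be verified by carbon monoxide at all times and "additionally at the 8, 10, 16, and 24-week interviews with saliva cotinine (see Table 2").

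The SAP (Tests of specific aims) analyses lapse and relapse with Cox proportional hazards models under Aim 1b. Under Aim 1a it gives week 24 as its example of a time point for comparing PPA. The Aim 1a power analysis assumes a PPA rate at the last follow-up and an average of five assessments per participant, put at 71% of those after quit date.

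**The concern.** The table and the text give different schedules for the instrument behind two of the three primary outcomes. Neither says where the first TLFB begins. Staff usually work from the schedule table. If they do so here and apply the written look-back, the first interview, at WK 8, starts at WK 4, and the weeks straight after quitting are never reconstructed day by day.

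Relapse is the more exposed outcome because it depends on a running count of smoking days. A count that starts late gives a late relapse date or none. The SAP plans ordinary Cox models and says nothing about event times known only to an interval.

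The blank PPA cells at WK 8-24 are a second, separate inconsistency. They concern the late visits and have no bearing on how early lapses are dated.

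**Working it through.** **1. Table 2 marks.** The table has 11 columns: pre-screen, screening, baseline, weeks 1-2, 3, 4, 5 (WK 0), 6 (WK 1), 7 (WK 2), 9 (WK 4) and 13-29 (WK 8, 10, 16, 24). All four smoking-outcome rows resolve to 11 cells, so nothing suggests a shifted column.

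| Row | Columns marked | Meaning |
|---|---|---|
| PPA | 3-10 | baseline to WK 4 |
| TLFB | 11 | WK 8, 10, 16, 24 |
| Carbon monoxide | 3-11 | baseline to WK 24 |
| Saliva cotinine | 10-11 | WK 4 to WK 24 |

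**2. Follow-ups in the text.** Quit week is protocol week 5, so WK = protocol week − 5. Weeks 9, 13, 15, 21 and 29 become WK 4, 8, 10, 16 and 24. Sections 3 and 4 also list 2 weeks after quit date.

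**3. Days with no TLFB,** out of 24 × 7 = 168, taking the look-back literally:

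| Reading | First TLFB | Reaches back to | Days uncovered |
|---|---|---|---|
| Table 2 | WK 8 | WK 4 | 1-28: 28/168 = 16.7% |
| Text, Compensation follow-ups | WK 4 | WK 2 | 1-14: 14/168 = 8.3% |
| Text, WK 2 also a follow-up | WK 2 | WK 1 | 1-7: 7/168 = 4.2% |
| WK 2 and WK 4, first one back to quit day | WK 2 | quit day | none |

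Only the last reading closes the gap, and the documents do not state it.

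**4. What the other records give.** Status at WK 1, 2 and 4 brackets a first lapse in intervals of 7, 7 and 14 days. A 7-day item at WK 4 covers days 22-28, so days 15-21 are not asked about directly.

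**5. Relapse.** Take a participant who smokes every day from day 1. The seventh smoking day is day 7. A count starting on day 29 puts it on day 29 + 6 = 35, which is 28 days late. A count starting on day 15 puts it on day 15 + 6 = 21, which is 14 days late. A participant who smokes on five days in days 1-28 and two days later has relapsed (5 + 2 = 7), but a count from day 29 shows only 2. Status reports do not repair this because they do not count days.

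**6. First lapse: illustrative power.** The documents give no lapse rates, so these inputs are assumptions: 40 per arm, 80% of placebo participants lapsing by day 168, 30%, 50% or 70% of those lapses by day 28, hazard ratio 0.5, log-rank test, 1,500 simulated trials.

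| Share of placebo lapses by day 28 | Exact dates | Early lapses dated to the WK 1, 2 or 4 visit | Same, participants lapsing in days 15-21 removed |
|---|---|---|---|
| 30% | 0.73 | 0.73 | 0.71 |
| 50% | 0.72 | 0.72 | 0.68 |
| 70% | 0.72 | 0.72 | 0.69 |

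If the status reports are used to bracket early lapses, little power is lost for first lapse.

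**7. PPA row.** The SAP's figure is 5 assessments = 71%. With k post-quit assessments, 5/k is 83% for k = 6, 71.4% for k = 7 and 62.5% for k = 8. Only k = 7 fits, that is WK 1, 2, 4, 8, 10, 16 and 24. Table 2 as printed gives three PPA assessments after quit week (WK 1, 2, 4), or four with WK 0. Both are below the assumed average of five.

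**The case against.** The strongest reply is that this is a mismatch between table and text, not a design that loses data. The text puts the TLFB at each follow-up, so WK 4 is covered and WK 2 perhaps is. The TLFB is retrospective, and the protocol does not define the previous assessment for the first interview, so that interview could run back to quit day. Other early records exist: weekly smoking status with carbon monoxide, self-monitoring from session 1 (Table 1), weekly therapist calls from quit date, and a patch rule that depends on daily cigarette counts.

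Much of this stands. A reader might infer from Table 2 that early lapses cannot be dated at all, or that power for time to first lapse collapses. The documents support neither. Status reports bracket many early first lapses, and a large loss of power appears only if every participant who lapses early is discarded, which nothing in the plan calls for.

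Two things remain. None of the other records is named as the source for the Cox models, and status reports cannot place the seventh smoking day. And the text alone does not close the gap: with the follow-ups listed under Compensation, days 1-14 still have no TLFB.

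On PPA, the text and SAP make clear that late collection is intended, so the blank cells look like missing marks. Table 2 was also read from a PDF by program; the cell counts are consistent, but the original should be checked.

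**Conclusion.** The concern holds as a contradiction between Table 2 and the text, with a real consequence for time to relapse. Under the stated look-back, the stretch with no day-level smoking record is days 1-28 if the table is followed, or days 1-14 if the text is followed with the Compensation list of follow-ups. Relapse cannot be located in that stretch from status reports, and a late-starting count can date it up to 28 or 14 days late, or miss it. For first lapse the effect is mainly coarser dating, in intervals of 7 to 14 days, and the power loss may be small; that rests on the assumed lapse pattern and on the status reports being used.

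The conclusion assumes that the look-back is applied literally and that the printed table matches the extracted one. It does not establish that data were lost, because the documents do not show which schedule staff followed.

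The blank PPA cells at WK 8-24 stand as a separate error in the table. A reader might infer that PPA is not collected at 24 weeks; the Smoking Status text, Aim 1a and the 5/7 = 71% figure all point the other way.

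**What to change.** - In Table 2, mark TLFB at the early post-quit visits already held (WK 1, 2 and 4) as well as at WK 8, 10, 16 and 24, so that it agrees with the Smoking Status text and the Compensation list of follow-ups.
- In section 5, state that the first TLFB reaches back to quit day and each later one to the last completed TLFB. A missed visit then leaves no hole.
- For participants already past WK 4, take the next TLFB back to quit day.
- Mark PPA at WK 8, 10, 16 and 24.

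The cost is an amendment to the table and two sentences of text, plus a few extra minutes of interview at visits that already take place. The downside is longer recall for participants already past WK 4: at the WK 8 interview, 56 days rather than 28.

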6-7	
 Continue NRT Provide support Anticipate high-risk situations Develop social support for nonsmoking Lifestyle changes (e.g., stress management, healthy diet, exercise, and increasing pleasant nonsmoking activities) 	
 Cognitive restructuring Interoceptive exposure Situational exposure (i.e., avoided situations) 	
 No

Nicotine Replacement Therapy (NRT). All participants will receive Nicoderm CQ®, 24-hour transdermal nicotine patches and will be educated about the use of the patch at the session immediately prior to quit date. They will be instructed to apply one patch daily, beginning on quit date (week 5). Participants will use the 3-step tapering Nicoderm process (21-mg, 14-mg, and 7-mg). This regimen has been used in previous trials with a similar formulation of the patch (Fiore, 2000). A meta-analysis found no differences in outcome between 16- or 24-hour patches (Fiore et al., 1994). Participants who continue to smoke or lapse after quit day will not be instructed to discontinue the patch until their smoking level reaches 4 cigarettes/day for 4 days. Smokers who lapse during treatment will be encouraged to set a new quit date and continue their cessation attempt.

D-cycloserine or Placebo Treatment. All capsules will be identical in appearance to maintain the blind design of the study. Study capsules will be prepared containing: (a) 250mg d-cycloserine or (b) pill placebo. Individual doses of study medications, prescribed by [name], will to be dispensed to patients by study personnel 1 hour prior to sessions 3-5 and patients will be asked to remain in the clinic until session time. Because all pill taking is observed, no pill counts are necessary to help ensure adherence to the randomized drug condition. All medications will be stored in a locked refrigerator.

A. LOCATION

All data will be collected at the University of Texas at Austin. Upon completion of data collection, data analysis will take place at UT, Southern Methodist University (PI: [name]), the University of Houston (PI: [name]), and Boston University (PI: [name]). All data will be encrypted with numeric codes so that no identifying information will be included in analyses. Drs. [name], [name] and [name] will obtain IRB approval from their respective institutions prior to accessing the data.

B. RESOURCES

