Treatment Credibility and Expectancy. The 18-item Treatment Credibility/Expectancy Questionnaire (CEQ; Devilly & Borkovec, 2000) will be used to examine whether treatment expectancy or credibility varied between PSRT+DCS and PSRT+PBO and the relationship between these constructs and treatment response. We will administer the scale after the first treatment sessions of PSRT+DCS and PSRT+PBO protocols.

Patient Adherence. Patient adherence will be assessed by taking attendance at each session. Adherence to the nicotine patch usage will be assessed at Weeks 1-8 following the quit date.

Therapist Adherence. Each session (for those participants who give consent to be videotaped) will be videotaped and 10% will be rated shortly thereafter by independent raters to assess therapist adherence to, and competence with, the treatment protocol. Participants are not required to be videotaped and will indicate on their consent form whether or not they are willing to participate in the recording of sessions.

Research Proposal

Concurrent Treatment. Use of medications other than nicotine patch or other aids to smoking cessation and participation in any concurrent psychotherapeutic treatment will be assessed at each assessment point.

Safety Monitoring and Concerns. At each visit, participants will be asked about side effects of the study medication, nicotine patches, and treatment. Adverse Events and Severe Adverse Events forms will be utilized to track any symptoms expressed during weekly check-ins. Forms will be reviewed each visit by the study PI, and participants who report significant symptoms or adverse reactions will be interviewed separately to determine whether the patch should be discontinued or the dose reduced. Participants who discontinue the patch or change the assigned dose will continue their treatment.

AlcoBreath Screening. At each of the three study visits during which participants are asked to take medication (sessions 3-5), participants will be asked to breathe into an AlcoBreath tube in order to assess for the presence of alcohol before they are administered the study medication.

Facial recognition task

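### The printed saliva cotinine cutoff (10 mg/ml) can never be exceeded; read as 10 ng/ml, it would be expected to count abstainers still wearing the trial's nicotine patch at week 8 as smokers

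*Protocol*

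**What the plan says.** Protocol section 5 defines 7-day point prevalence abstinence (PPA) and bases the main outcome analyses on it. Two paragraphs there govern how a report of abstinence is checked.

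- **Biochemical Verification.** For the four visits from post-quit week 8 to week 24, a report of abstinence "will be verified by saliva cotinine (cutoff value of 10 mg/ml) for stated abstinence of 2 weeks or more". Expired carbon monoxide (CO) is assigned to shorter claims: "carbon monoxide analysis of breath samples (8ppm cutoff) for stated abstinence of 24 hours to 2 weeks". The decision rule is "Detected values above the stated cutoff scores will be considered indicative of smoking".
- **Smoking Status.** "Participant reports of abstinence at all times will be verified by expired carbon monoxide, and additionally at the 8, 10, 16, and 24-week interviews", where saliva cotinine is added. Then: "Self-report will be overridden by objective verification in the conservative direction".

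On the patch, section 4 (Nicotine Replacement Therapy) gives every participant in both arms 24-hour nicotine patches. One is worn each day from the quit date, stepping down through 21, 14 and 7 mg. The length of each step is not given. Section 5 (Patient Adherence) adds: "Adherence to the nicotine patch usage will be assessed at Weeks 1-8 following the quit date".

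The SAP (Overview) models PPA over time and allows a comparison of the arms at any assessment. Neither document says how to read a cotinine value from someone using a patch.

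**The concern.** Cotinine is formed from nicotine whatever the source. A test that separates smokers from abstainers by cotinine therefore needs a rule for people taking nicotine as trial treatment, and none is given. The cutoff is wrong in different ways under the two possible readings. As printed, the test can detect nobody. In the unit presumably meant, it would be expected to flag true abstainers who are still using the patch as instructed. A clean CO reading does not rescue them, because Smoking Status adds cotinine to CO and lets a positive objective result replace self-report.

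At stake is the recorded week-8 value of one of the three primary outcomes, in a trial meant to supply effect-size data for a larger one. PPA would be understated in both arms and the week-8 contrast attenuated and less precise. If patch use among abstainers differed by arm, the contrast would also be biased.

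**Working it through.** **1. The printed unit.** 10 mg/ml × 1,000,000 = 10,000,000 ng/ml. At that concentration 2.1 ml of saliva would hold the whole nicotine content of a 21 mg daily patch (21 ÷ 10). The cutoff is stated without a derivation, so there is nothing further to reproduce.

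**2. Read as 10 ng/ml: cotinine from the patch alone.** Steady-state level = nicotine per minute × share converted × molecular-weight ratio ÷ clearance. Assumptions, none of them from the documents: the full labelled dose is delivered, conversion is 0.5 to 1.0, the molecular-weight ratio is 1.086, clearance is 20 to 200 ml/min, and saliva is about equal to plasma. For the lowest step, 7 mg/day = 7,000,000 ÷ 1,440 = 4,861 ng/min.

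- Low end: 4,861 × 0.5 × 1.086 ÷ 200 = 13 ng/ml.
- High end: 4,861 × 1.0 × 1.086 ÷ 20 = 264 ng/ml.
- The same ranges are 26 to 528 ng/ml for 14 mg and 40 to 792 ng/ml for 21 mg.

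Every value exceeds 10 ng/ml. To fall to 10 on the 7 mg patch at 50% conversion, clearance would have to reach 264 ml/min, above the assumed range.

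**3. Which visits.** Adherence checks run to post-quit week 8, so patch use at the week-8 cotinine visit is supported. Week 10 is possible, because step lengths are not stated. Weeks 16 and 24 are not shown to be affected.

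**4. Size at week 8.** Inputs: 43% and 27%, the SAP's last-follow-up rates borrowed for week 8 (ω = 0.08 ÷ √(0.35 × 0.65) = 0.168, matching the SAP's .17); 40 per arm, half of 80. Let *a* be the share of true abstainers still on the patch and *s* the share of abstainers stating 2 weeks or more. Recorded PPA = p(1 − *a·s*). SE(log OR) = √[1/(40p₁(1−p₁)) + 1/(40p₀(1−p₀))]. Power is for a two-sided 5% Wald test at that visit.

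Without patch use: SE = √(1/9.804 + 1/7.884) = 0.478.

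| *s* | *a* | DCS vs placebo | OR | SE | Power |
|---|---|---|---|---|---|
| – | 0 | 43.0% vs 27.0% | 2.04 | 0.478 | 0.32 |
| 0.8 | 0.3 | 32.7% vs 20.5% | 1.88 | 0.517 | 0.23 |
| 0.8 | 0.5 | 25.8% vs 16.2% | 1.80 | 0.561 | 0.18 |
| 0.8 | 0.7 | 18.9% vs 11.9% | 1.73 | 0.634 | 0.14 |
| 0.6 | 0.5 | 30.1% vs 18.9% | 1.85 | 0.531 | 0.21 |
| 1 (upper bound) | 0.5 | 21.5% vs 13.5% | 1.75 | 0.602 | 0.15 |
| 1 (upper bound) | 0.7 | 12.9% vs 8.1% | 1.68 | 0.747 | 0.11 |

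At *a* = 0.5, *s* = 0.8, about 7 of 17 abstainers on DCS and 4 of 11 on placebo are recoded (17.2 × 0.4 = 6.9; 10.8 × 0.4 = 4.3).

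Unequal patch use, *s* = 0.8: *a* = 0.5 on DCS and 0.3 on placebo gives OR 1.35; the reverse gives 2.51.

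**5. Effect on the modelled tests.** I fitted a marginal logistic model to expected proportions at weeks 1, 2, 4, 8, 10, 16 and 24, with quadratic time, treatment and treatment × time, time centred at 24, flat 43% and 27% except at week 8, and visits treated as independent. This is a simplification of the SAP's mixed model. At *a* = 0.5 in both arms the week-24 OR goes from 2.04 to 2.01 (*s* = 1) or 2.02 (*s* = 0.8). The slope difference shifts by 0.0007 or 0.0006, against an SE of 0.024 with all visits attended, or 0.028 with five of seven attended.

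**The case against.** The strongest reply is that little depends on this. Aim 1a tests slopes and PPA at a chosen time, with week 24 as the SAP's example, and step 5 shows that both are nearly unmoved. What is left is a week-8 contrast that the SAP merely permits, with power of only 0.32 even when coded perfectly, in a study whose stated goals are feasibility and whether to go on. Misclassification should be similar in both arms. **This stands**, and it limits the seriousness of the point.

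Second, the two faults need opposite readings of the unit, and a laboratory would be unlikely to apply mg/ml literally. The readings are indeed alternatives, but the rule fails under each, and correcting the unit alone brings the patch problem into force.

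Third, the size rests on unknowns. Adherence checks at weeks 1 to 8 would also fit patches ending just before the visit, and the number recoded could then be near zero. This stands for the size. The direction holds across the whole range of cotinine levels in step 2.

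Fourth, a patch exemption swaps cotinine for a test with a shorter detection window, and a relapsed smoker who reports patch use could benefit. That is a real cost, confined to visits with recorded nicotine-product use.

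Finally, Table 2 appears to mark saliva cotinine at post-quit week 4 as well, which the text does not. If that mark is real, the problem is wider than week 8. It is not counted above.

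**Conclusion.** The concern holds and should be fixed. The printed cutoff makes the cotinine check inoperative. Under the 10 ng/ml reading, which is an assumption, the stated rule would be expected to code true abstainers wearing the trial patch at week 8 as smokers. With equal patch use in the two arms, the illustrated week-8 odds ratio falls from 2.04 to between 1.68 and 1.88, and single-visit power from 0.32 to between 0.11 and 0.23. These figures depend on borrowed PPA rates, 40 per arm, and patch and abstinence-duration shares that the documents do not give. No bias toward one arm is expected unless patch use among abstainers differs by arm. The modelled week-24 and slope tests are essentially unaffected. Time to lapse and time to relapse come from the timeline follow-back and are not defined by this rule. If mg/ml were applied literally, the remaining safeguard would be CO, provided that Smoking Status and the CO marks in Table 2 govern rather than the narrower CO role in Biochemical Verification.

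**What to change.** 1. Correct the unit of the cotinine cutoff and tie it to one assay. Section 5 names a radioimmune assay and section 7 an enzyme immunoassay; no effect of that difference on PPA is shown.
2. Pre-specify that at any cotinine visit where use of the patch or another nicotine product in the previous 2 weeks is recorded, abstinence is verified by expired CO at the stated 8 ppm, and cotinine above the cutoff does not override self-report. Keep cotinine for everyone else.
3. Reconcile Smoking Status with Biochemical Verification on when CO applies, and reconcile both with the apparent week-4 cotinine mark in Table 2.
4. Confirm that the Patient Adherence record captures patch use at the week 8 to 24 visits. Table 2 marks it there, but the table note says its schedule will vary. Add a question only if it does not.

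The cost is a unit correction and one coding rule. CO is already scheduled at these visits, so new data are needed only if item 4 fails. The price is CO's shorter detection window among participants with recorded nicotine-product use. No change to treatment is involved.
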